Progression: 25% increase in the sum of products of all measurable lesions over **smallest sum observed during treatment** (which may be smaller than baseline) using the same techniques as baseline, OR clear worsening of any non-measurable disease, OR appearance of any new lesion/site, OR clear clinical worsening or failure to return for evaluation due to death or deteriorating condition (unless clearly unrelated to this cancer).

Unknown: Progression has not been documented and one or more measurable or non-measurable site(s) have not been assessed.

Best Overall Response: For patients with all disease sites assessed every evaluation period, the best response will be defined as the best objective status as measured according to [Section 11.4](#). If the response does not persist on an MRI at least 1 month later, the response will still be recorded based on the prior scan, but will be designated as a non-sustained response. If the response is sustained, e.g. still present on the subsequent MRI, it will be recorded as a sustained response, lasting until the time of tumor progression. Best response is unknown if the patient did not have measurable disease either at study entry or post-operatively for patients on the surgical substudy of phase II or if all objective status determinations before progression are unknown.

12 DATA REPORTING / REGULATORY REQUIREMENTS

Adverse event lists, guidelines, and instructions for AE reporting can be found in [Section 7.0](#) (Adverse Events: List and Reporting Requirements).

12.2 CTEP Multicenter Guidelines: N/A

12.3 Cooperative Research and Development Agreement (CRADA)/Clinical Trials Agreement (CTA)

The agent(s) supplied by CTEP, DCTD, NCI used in this protocol is/are provided to the NCI under a Collaborative Agreement (CRADA, CTA, CSA) between the Pharmaceutical Company(ies) (hereinafter referred to as "Collaborator(s)") and the NCI Division of Cancer Treatment and Diagnosis. Therefore, the following obligations/guidelines, in addition to the provisions in the "Intellectual Property Option to Collaborator" (<http://ctep.cancer.gov/industry>) contained within the terms of award, apply to the use of the Agent(s) in this study:

1. Agent(s) may not be used for any purpose outside the scope of this protocol, nor can Agent(s) be transferred or licensed to any party not participating in the clinical study. Collaborator(s) data for Agent(s) are confidential and proprietary to Collaborator(s) and shall be maintained as such by the investigators. The protocol documents for studies utilizing investigational Agents contain confidential information and should not be shared or distributed without the permission of the NCI. If a copy of this protocol is requested by a patient or patient's family member participating on the study, the individual should sign a confidentiality agreement. A suitable model agreement can be downloaded from: <http://ctep.cancer.gov>.
2. For a clinical protocol where there is an investigational Agent used in combination with (an)other investigational Agent(s), each the subject of different collaborative agreements , the access to and use of data by each Collaborator shall be as follows (data pertaining to such combination use shall hereinafter be referred to as "Multi-Party Data."):
 - a. NCI will provide all Collaborators with prior written notice regarding the existence and nature of any agreements governing their collaboration with NIH, the design of the proposed combination protocol, and the existence of any obligations that would tend to restrict NCI's participation in the proposed combination protocol.
 - b. Each Collaborator shall agree to permit use of the Multi-Party Data from the clinical trial by any other Collaborator solely to the extent necessary to allow said other Collaborator to develop, obtain regulatory approval or commercialize its own investigational Agent.

6. Any manuscripts reporting the results of this clinical trial must be provided to CTEP by the Group office for Cooperative Group studies or by the principal investigator for non-Cooperative Group studies for immediate delivery to Collaborator(s) for advisory review and comment prior to submission for publication. Collaborator(s) will have 30 days from the date of receipt for review. Collaborator shall have the right to request that publication be delayed for up to an additional 30 days in order to ensure that Collaborator's confidential and proprietary data, in addition to Collaborator(s)'s intellectual property rights, are protected. Copies of abstracts must be provided to CTEP for forwarding to Collaborator(s) for courtesy review as soon as possible and preferably at least three (3) days prior to submission, but in any case, prior to presentation at the meeting or publication in the proceedings. Press releases and other media presentations must also be forwarded to CTEP prior to release. Copies of any manuscript, abstract and/or press release/media presentation should be sent to:

Email: [contact]

The Regulatory Affairs Branch will then distribute them to Collaborator(s). No publication, manuscript or other form of public disclosure shall contain any of Collaborator's confidential/proprietary information.

An accounting will be done of all patients registered in the study. The number of patients who died or withdrew before treatment began will be specified. Patients who did not meet all eligibility criteria will be described. Patients who were evaluated separately due to first-cycle non-drug-related death or cessation of first-cycle therapy prior to DLT will be characterized. Treatment administration will be described for all cycles. Doses administered, dose modifications or delays, and duration of therapy will be evaluated. Safety variables will be summarized by descriptive statistics. Adverse events that occur will be reported for each dose level and described in terms of incidence and severity. Laboratory data will be presented by dose level at each observation time. Values outside of normal limits will be identified and their frequency calculated. Parameters will be described based on the CTCAE version 4.0 severity grading. Distribution by CTC severity grade (when applicable) and clinical relevance will be given.

Phase II:

The primary clinical objective of this phase of the study will be to determine if temsirolimus and perifosine in combination can significantly delay progression and/or induce tumor responses in patients with recurrent malignant gliomas. The trial cohort will include both GBM and Anaplastic Glioma (AG) patients. The primary endpoint is a hybrid endpoint of progression-free survival (PFS) at 6 months and radiographic response. The calculation of PFS for patients will be determined from the first day of study drug administration except for those in the surgical substudy for whom it will be calculated from the first day of study drug administration following surgery.

The historical values for comparison are from a database of 225 GBM patients enrolled in 8 previous phase II studies (in which none of the treatments were considered particularly effective). (Wong, Hess et al. 1999) In this database, the 6 month PFS was 15% for GBM. The 6 month PFS for patients treated with BCNU for recurrence/progression was 17.5%. (Brandes, Tosoni et al. 2004) Therefore, we would expect 6 month PFS to be less than 20% in molecular unselected recurrent GBMs.

At the end of the second stage, if ≤ 9 patients with GBM reach 6 months of progression-free survival, then, we will conclude that the treatment is not sufficiently active in recurrent/progressive GBMs. The design has power 0.90 for a population success proportion of 0.45/0.35 in the enriched/nonenriched populations, using a 0.10 size test for success rates of 0.25/0.15 in the enriched/nonenriched populations.

In addition to the assessment of the population success rate in this population, the crude incidence rates for the probability of remaining alive and progression free for six months, patient response, and toxicity will be computed along with the attendant 95% confidence intervals. Kaplan-Meier estimates of the progression-free and overall survival distributions will be computed as a function of time in the whole group and stratified by molecular profile.

Although it is estimated that 25% of patients will be enriched patients, we do not stratify accrual based on this factor. If the treatment regimen appears promising given the observed mixture of enriched/nonenriched patients then additional patients may be accrued in order to obtain 10 enriched patients. Outcomes (e.g., response, progression rate, toxicity) will be summarized descriptively for these patients.

Anaplastic gliomas

Up to 10 patients with anaplastic gliomas will be accrued to the phase II study. Endpoints such as response, median overall survival, and median progression-free survival will be computed in order to gain preliminary data for these other malignant glioma subtypes. However, the historical controls for patients with anaplastic glioma are less well defined than for GBM; therefore, only patients with GBM will be included in analyses of efficacy. Archival tissue will be profiled to explore whether profiling influences response in such patients.

Prior treatment with bevacizumab or other direct inhibitors of VEGF/VEGFR including Aflibercept (VEGF-Trap) and cediranib and XL-184 (BMS 907351).

In order to obtain specimens for study of molecular effects of drug therapy in tumor tissue, we plan to accrue up to 10 subjects to a preoperative treatment arm. Although patients on the surgical substudy will have resections of tumor at the initiation of treatment, the natural history of recurrent GBM strongly supports the concept that nearly all patients will have tumor progression by 6 months if no further treatment or ineffective treatment is provided post-operatively. For example, a review of patients with recurrent GBM treated for first relapse at the MD Anderson Cancer Center also supports the concept that gross total resection does not impact on 6-month PFS rate. During the time from of 2001-2003, 220 patients were treated at MD Anderson for first relapse or progression of GBM. There was no difference in 6-month PFS between those patients who had a gross total resection at relapse compared with all other patients. ([name], personal communication). Hence, we plan to combine data from patients on and not on the surgical substudy in efficacy analyses. The calculation of PFS for patients enrolled in the pre-operative component of the study will be determined from the first day of study drug administration following surgery.

Molecular profiling of pre-treatment tissue

perifosine sensitivity. Such sequencing is crucial because it is an emerging paradigm that mutations in the genes encoding the targets of small molecule inhibitors can sensitize those targets to their inhibitors including mTOR inhibitors such as temsirolimus in myeloma (Shi *et al.*, 2002) and GBM (Smith *et al.*, 2002) as MSKCC investigators have demonstrated in both non-small cell lung cancer (Pao *et al.*, 2004) and glioblastoma (Mellinghoff *et al.* 2005; Cloughesy *et al.* 2007)

We hypothesize that patients who respond to combination therapy of temsirolimus and perifosine or with at least 6 months of progression free-survival will have pre-treatment tumor tissue exhibiting high levels of AKT and RAS/ERK signaling because we hypothesize that these targets must be active for drug action, and because these signal transduction cascades are activated in the mouse GBM model system used in the ascertainment of the preclinical data. As above, we hypothesize that tumors exhibiting a PDGF-like molecular profile may also exhibit greater sensitivity to the study treatment because the mouse GBM model used is a PDGF-ligand driven tumor.

Molecular effects during treatment

The evaluation of the *in vivo* biological activity of these agents will be based on a within patient comparison of PI3K/AKT/mTOR/S6K signaling and cell proliferation in pre-treatment archived tissue to the tissue acquired during treatment as part of the phase II surgical substudy. The therapy will be considered molecularly effective if the phosphorylation of PI3K/AKT/mTOR/S6K is decreased by at least level by immunohistochemistry (and Western blot when sufficient frozen tissue is available for analysis) based on the pathology grading for those markers which are positive in the pretreatment tissue for that patient. (See discussion of the assays to be used in the [laboratory correlates section](#).) Effects on proliferation will be assessed by counting mitoses on standard H&E staining, and by Ki-67 immunostaining to estimate the proliferation index (% of tumors staining per HPF). Effects on apoptosis (TUNEL) will also be analyzed in paraffin embedded tissue. Tissue data will be compared to data from our perifosine monotherapy trial (analysis underway) to determine molecular correlates of perifosine alone versus perifosine + temsirolimus. Given the small number of patients (maximum 10) who will undergo surgery, these studies will also be considered exploratory.

13.4 Analysis of Secondary Endpoints

Radiographic response rate will be reported according to the definitions above ([Section 11.4](#)). This will be reported using all eligible patients who receive at least 1 dose of protocol therapy with temsirolimus and/or perifosine, and another [section](#) will detail the response rate for evaluable patients only (those with measurable disease at study entry or post-operatively among those enrolled on the phase II surgical substudy). A response rate analysis on this subset will include an explanation of which patients were excluded from the analysis and for which reasons. Calculations of 95% confidence limits will be given where applicable. Median overall and progression-free survival will be calculated and include all eligible patients who received at least 1 dose of protocol therapy with temsirolimus and/or perifosine. Biologic correlative goals include molecular analysis of pre-treatment tissue to identify both molecular predictors of response (using Fishers exact test) and molecular effects during treatment (using Wilcoxon rank sum test) as described in [section 2.5](#) and [section 9](#).

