An important limitation of prior studies of targeted molecular agents in GBMs is the lack of tumor tissue to determine whether the therapeutic agents under evaluation inhibited their putative molecular targets. We previously demonstrated such analyses are possible through a surgical substudy in which patients who undergo cytoreductive surgery for recurrent disease receive study drug pre-operatively and then restart the agents upon recovery from surgery.([name] *et al.* 2005) Therefore, in this study up to 10 patients enrolling into the phase II component will undergo resection of their tumor as part of the trial. These patients will receive temsirolimus and perifosine pre-operatively at the dose determined by the phase I. Tumor specimens resected in this manner will be analyzed for evidence of inhibition of PI3K/AKT/mTOR/S6K and RAS/MEK/ERK signaling by immunohistochemistry of

Amended:

Reviewed by OCR, JR 3/24/14

Memorial Sloan Kettering Cancer Center
IRB Protocol

IRB#: 09-058 A(14)

paraffin embedded tissue and Western blot of flash frozen tissue. PTEN, p-AKT, p-mTOR, total S6K, p-S6K, p-ERK, Ki-67, and apoptosis will be measured. These data will be compared to similar analysis performed on tumor tissue not exposed to temsirolimus and perifosine obtained from each patient's original or prior surgery (intra-patient comparison). After recovery from surgery, patients will resume treatment with temsirolimus and perifosine. Treatment duration will be measured in 4 week cycles.

Phase I and II

Patients will remain on treatment as long as there are no unacceptable toxicities until tumor progression. Responses will be assessed by MRI scans every 8 weeks. Fluorodeoxyglucose (FDG)-PET will be performed in phase II patients to evaluate the effects of the drugs on tumor metabolism. Paraffin tumor sections from the original surgical resection will be obtained from all patients. An attempt will be made to correlate the genotype patient's tumor specimens with response to treatment. In this way, molecular subsets of malignant gliomas that may be more or less likely to respond to treatment with temsirolimus and perifosine can be identified.

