In addition, a subset of patients on the phase II study will receive dual drug therapy followed by surgical resection of tumor. This provides an opportunity to assess the molecular effects of therapy in humans *in vivo*. We will perform the above analysis for PI3K/AKT/mTOR/S6K and RAS/MEK/ERK signaling, proliferation, and apoptosis, using intrapatient comparison from pre-treatment archival tissue from an earlier resection as we have done in other studies. ([name] *et al.*, 2005)

Amended:

Reviewed by OCR, JR 3/24/14

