FISH analysis will be performed in the FISH laboratory in the Pathology Department at Memorial Sloan Kettering Cancer Center and other assays in the laboratories of [name] and [name], PhD at Memorial Sloan Kettering Cancer Center or their designee(s).

The following studies will be performed:

- FISH for *EGFR* amplification, *PDGFRA* amplification, and *NF1* loss and others
- Immunohistochemistry for *NF1* under-expression, PDGF ligand, *PTEN*, *AKT*, *pAKT*, *mTOR*, *p-mTOR*, *S6K*, *pS6K*, *ERK*, *pERK*, and *Ki67* and others
- Western blot of homogenized flash frozen tissue (when available) for *NF1*, *PDGF* (ligands), *PTEN*, *AKT*, *pAKT*, *S6K*, *pS6K*, *ERK*, *pERK*, and proliferating cell nuclear antigen (PCNA) and others if immunohistochemistry fails for these markers.
- TUNEL

If sufficient tissue is available (paraffinized and/or frozen), we will also perform

- RNA extraction for RTPCR analysis of *DLL3*, *SOX4*, *NCAM1*, and Doublecortin overexpression and others
- DNA extraction for mutational analysis of *PTEN*, *AKT*, *PI3K*, *mTOR*, *EGFR*, *NF1*, and others

9.1.2 *Molecular effects during treatment*

The evaluation of the in vivo biological activity of these agents will be based on a within patient comparison of *PI3K/AKT/mTOR/S6K* signaling and cell proliferation in pre-treatment archived tissue to the tissue acquired during treatment as part of the phase II surgical substudy. The therapy will be considered molecularly effective if the phosphorylation of *PI3K/AKT/mTOR/S6K* is decreased by at least one level based on the pathology grading for those markers which are positive in the pretreatment tissue for

Amended:

Reviewed by OCR, JR 3/24/14

Memorial Sloan Kettering Cancer Center
IRB Protocol

IRB#: 09-058 A(14)

that patient. (See discussion of the assays to be used in the [laboratory correlates section](#).) Given the small number of patients who will undergo surgery, these studies will also be considered exploratory.

9.1.2.1 *Collection of Specimen(s):*
see [section 5.1.3.2](#)

9.1.2.2 *Handling of Specimens(s):*
see [section 5.1.3.2](#)

9.1.2.3 *Shipping of Specimen(s):*

Not applicable (all resections on the surgical substudy will occur at Memorial Sloan Kettering Cancer Center)

9.1.2.4 *Site Performing Correlative Study:*

All assays will be performed in the laboratories of [name] and [name], PhD at Memorial Sloan Kettering Cancer Center or their designee(s).

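### Section 13.4 names the two-sample Wilcoxon rank sum test for on-treatment molecular effects that sections 2.5 and 9 define as a within-patient comparison

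*Combined protocol and SAP*

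**What the plan says.** Section 13.4 (Analysis of Secondary Endpoints) gives Fisher's exact test for molecular predictors of response, then continues: "and molecular effects during treatment (using Wilcoxon rank sum test". It refers to sections 2.5 and 9 for what is being compared.

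- Section 2.5 describes the surgical-substudy tissue analysis as "using intrapatient comparison from pre-treatment archival tissue from an earlier resection".
- Section 9.1.2 says the evaluation of in vivo activity "will be based on a within patient comparison of" signaling and proliferation before and during treatment. It calls therapy molecularly effective if phosphorylation is "decreased by at least one level based on the pathology grading", applied to "those markers which are positive in the pretreatment tissue".
- Section 2.4 takes the untreated comparator from each patient's "original or prior surgery (intra-patient comparison").
- Section 13.1 repeats the within-patient definition. It also plans a comparison with tissue from the perifosine monotherapy trial.

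The number of pairs is capped. Section 2.4 says "up to 10 patients enrolling into the phase II component will undergo resection", and 13.1 says "we plan to accrue up to 10 subjects to a preoperative treatment arm". Sections 9.1.2 and 13.1 both call the work exploratory. Under 13.1, immunohistochemistry and Western blot are scored 0-3 and Ki-67 is a percentage index.

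**The concern.** Before-and-during samples from the same patient are not independent, yet the named test treats them as if they were. It discards the pairing that the preoperative dosing and the archival-tissue requirement make possible. If a patient's two values are positively correlated, the rank sum test uses too large a variance and becomes conservative. A real fall in a continuous marker such as Ki-67 could then be reported as no evidence of effect. An analyst following 13.4 literally would run the wrong test. One who noticed the problem would have to choose another after seeing the data.

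**Working it through.** **Which comparison fits which test**

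| Comparison | Where described | Structure | Test named |
|---|---|---|---|
| Archival vs on-treatment tissue, same patient | 2.4, 2.5, 9.1.2, 13.1 | paired, at most 10 | rank sum (13.4) |
| This trial's tissue vs perifosine monotherapy trial | 13.1 only | independent groups | none stated |
| One-level fall per patient | 9.1.2, 13.1 | paired, a classification | none, no p-value |

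The rank sum test suits the second row, but 13.4 attaches it to the sections that describe the first.

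**Why pairing matters.** With common SD σ and within-patient correlation ρ, the mean difference over n pairs has variance 2σ²(1−ρ)/n. A two-sample test works as if it were 2σ²/n. At ρ = 0.5 the true variance is 1 − 0.5 = 0.5 of that assumed, and at ρ = 0.7 it is 0.3.

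**Size.** The plan states no power, alpha, effect size or correlation for this analysis, so there is no figure of its own to reproduce. Assumed inputs: two-sided 0.05, a 1-SD fall, ρ from 0 to 0.7, bivariate normal values, and the 0-3 score formed by cutting at −1, 0 and 1. There were 10,000 simulated trials per setting (Monte Carlo SE at most 0.005). The signed-rank test is exact. The rank sum test is exact for the continuous marker and a tie- and continuity-corrected normal approximation for the score. Each cell is signed-rank / rank sum.

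Power, continuous marker:

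| Pairs | ρ = 0 | 0.3 | 0.5 | 0.7 |
|---|---|---|---|---|
| 10 | 0.49 / 0.51 | 0.64 / 0.52 | 0.78 / 0.52 | 0.94 / 0.54 |
| 8 | 0.35 / 0.44 | 0.46 / 0.43 | 0.62 / 0.44 | 0.82 / 0.45 |
| 6 | 0.20 / 0.31 | 0.27 / 0.28 | 0.35 / 0.27 | 0.54 / 0.27 |

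Power, 0-3 score:

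| Pairs | ρ = 0 | 0.3 | 0.5 | 0.7 |
|---|---|---|---|---|
| 10 | 0.34 / 0.48 | 0.42 / 0.48 | 0.50 / 0.47 | 0.63 / 0.48 |
| 8 | 0.20 / 0.37 | 0.24 / 0.35 | 0.29 / 0.36 | 0.38 / 0.35 |
| 6 | 0.05 / 0.26 | 0.06 / 0.24 | 0.06 / 0.22 | 0.07 / 0.21 |

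Type I error, 10 pairs:

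| Scale | ρ = 0 | 0.3 | 0.5 | 0.7 |
|---|---|---|---|---|
| Continuous | 0.052 / 0.047 | 0.048 / 0.019 | 0.047 / 0.009 | 0.049 / 0.002 |
| 0-3 score | 0.026 / 0.047 | 0.017 / 0.022 | 0.014 / 0.010 | 0.009 / 0.003 |

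An exact permutation rank sum test on the score has slightly lower power: 0.44 / 0.44 / 0.43 / 0.42 across the four correlations with 10 pairs. Other cut points (−0.67, 0, 0.67) with a 0.8-SD fall and 10 pairs show the same pattern for signed-rank / rank sum: 0.27 / 0.30 at ρ = 0.3, 0.31 / 0.28 at 0.5, and 0.42 / 0.27 at 0.7.

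**Worked example.** Ten baseline-positive patients score 3,3,3,2,2,2,2,1,1,1. The first eight fall one level and the last two do not change. Signed-rank: eight non-zero differences, all in one direction, so p = 2/2⁸ = 0.008. Rank sum on the same data: exact p = 0.051, or 0.038 by normal approximation.

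**Floor of the signed-rank test.** With m non-zero differences the smallest two-sided p is 2/2^m: 0.0625 at m = 5 and 0.031 at m = 6. With five or fewer it cannot reach 0.05.

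**The case against.** The plan's own conclusion about molecular effect does not use this test. It rests on the one-level rule, which is already paired and carries no p-value. No decision or error rate is attached to the rank sum test, and the work is declared exploratory. That stands, and it limits the point to a minor one.

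The replacement is also not uniformly better. Most of the markers are scored 0-3. On that scale the signed-rank test has less power at correlation 0.3 or below with 10 pairs, at 0.5 or below with 8, and at every correlation tried with 6. Low correlation is plausible, because the archival sample may come from the original surgery and 13.1 itself warns about intervening treatment. Usable pairs may be fewer than 10, since the one-level rule counts only markers positive at baseline. All of this stands. The power argument is therefore confined to continuous measures at moderate or higher correlation. For the score, the proportion meeting the one-level rule is the more useful summary, and an exact sign test would respect the pairing equally well.

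The rank sum test may have been meant for the monotherapy-trial comparison. If so, 13.4 points to the wrong sections and the within-patient comparison has no test, so the text needs correction either way.

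**Conclusion.** The concern holds, as a minor point. Section 13.4 names a test for independent samples for a comparison that the sections it cites define as paired. Among the on-treatment comparisons, the test fits only the cross-trial one in 13.1.

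In the settings simulated (correlation 0 to 0.7), the rank sum test does not inflate type I error, so the risk is a missed effect. That risk is material for a continuous marker: with 10 pairs the power difference is 0.78 − 0.52 = 0.26 at correlation 0.5 and 0.94 − 0.54 = 0.40 at 0.7. It disappears at correlation 0. These sizes rest on an assumed 1-SD fall, an assumed correlation and a 0.05 level, none of which the plan gives. The simulation does not model the restriction to baseline-positive markers. The primary decision rule, sample size and patient management are unaffected.

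**What to change.** In section 13.4:

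1. For pre-treatment versus on-treatment tissue, replace the rank sum test with the exact Wilcoxon signed-rank test on within-patient differences.
2. For each marker, report the number and proportion of baseline-positive patients who meet the one-level criterion of 9.1.2, with a Clopper-Pearson 95% interval. For example, 7 of 10 gives 0.348 to 0.933, and 5 of 8 gives 0.245 to 0.915. This stays informative when there are too few non-zero differences for the signed-rank test to reach 0.05.
3. Keep the rank sum test only for the unpaired comparison with the perifosine monotherapy trial, and cite 13.1 for it.

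The cost is one phrase and one descriptive line, with no extra data and no burden on patients. The statistical cost is lower power for the signed-rank test on the 0-3 score when correlation is low or pairs are few. On a continuous marker it also has less power at correlation 0 with 8 or 6 pairs. Item 2 covers the coarse score in those cases.
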